 5. LDH
 6. Alkaline Phosphatase

The results of these laboratory tests must be reported to BI as soon as possible.

If the initial alert values (ie AST,ALT, and bilirubin) are confirmed on the second sample described as above, then an abdominal ultrasound or clinically appropriate alternate imaging (to rule out biliary tract, pancreatic or intrahepatic pathology, e.g. bile duct stones or neoplasm) must be completed within 48 hours.

The findings from the hepatic imaging (including comparison to prior imaging if available) must be made available as soon as possible as part of the adverse event reporting process. In the event the etiology of the abnormal liver tests results is not identified based on the imaging (e.g. biliary tract, pancreatic or intrahepatic pathology), then the “DILI checklist” must be completed. Details of the “DILI checklist” are provided in the ISF. The following assessments need to be performed in order to complete the “DILI checklist”. Any resulting diagnoses will be reported via the eCRF:

- obtain a detailed history of current symptoms and concurrent diagnoses and medical history according to the “DILI checklist” provided in the ISF;
- obtain history of concomitant drug use (including non-prescription medications, herbal and dietary supplement preparations), alcohol use, recreational drug use, and special diets according to the “DILI checklist” provided in the ISF;
- obtain a history of exposure to environmental chemical agents (consider home and work place exposure) according to the “DILI checklist” provided in the ISF;

- complete the following laboratory tests as detailed in the DILI checklist provided in the ISF:
 - *Clinical chemistry*
alkaline phosphatase, cholinesterase (serum)*, albumin, PT or INR, CK, CK-MB, coeruloplasmin*, α -1 antitrypsin*, transferrin*, amylase, lipase, fasting glucose, cholesterol, triglycerides
 - *Serology*
Hepatitis A (Anti-IgM, Anti-IgG), Hepatitis B (HbsAg, Anti-HBs,DNA), Hepatitis C (Anti-HCV, RNA if Anti-HCV positive), Hepatitis D (Anti-IgM, Anti-IgG), Hepatitis E (Anti-HEV, Anti-HEV IgM, RNA if Anti-HEV IgM positive), Anti-Smooth Muscle antibody (titer), Antinuclear antibody (titer), Anti-LKM (liver-kidney microsomes) antibody, Anti-mitochondrial antibody, Epstein Barr Virus (VCA IgG, VCA IgM), cytomegalovirus (IgG, IgM), herpes simplex virus (IgG, IgM)*, varicella (IgG, IgM)*, parvovirus (IgG, IgM)*
 - *Hormones, tumormarker*
Thyroid-stimulating hormone(TSH)*
 - *Haematology*
Thrombocytes, eosinophils
*If clinically indicated (e.g immunocompromised patients)

Long term follow-up

- Initiate close observation of subjects by repeat testing of ALT, AST, and bilirubin (with fractionation to total and direct) at least weekly until the laboratory ALT and or AST abnormalities stabilize or return to normal, then according to the protocol. Depending on further laboratory changes, additional parameters identified e.g. by reflex testing will be followed up based on medical judgement and Good Clinical Practices (GCP).

Report any resulting diagnoses via the eCRF.

10.5 APPENDIX 5: RECIST 1.1 CRITERIA

The criteria below are based on RECIST 1.1 ([R09-0262](#)).

The preferred method of assessment is a spiral CT scan with IV and oral contrast, unless IV and/or oral contrast are medically contraindicated. CT scans of the chest, abdomen and other areas of known or newly suspected disease must be performed. Scans of the abdomen, pelvis and other areas of the body, but not chest, may be done with MRI instead of CT.

Skin lesions followed as target lesions must be documented by colour digital photography and must include in the image a ruler with millimetre subdivisions and a label that includes the patients ID and date.

Bone scans (using ^{99m}m-technetium polyphosphonate scintigraphy) are recommended at baseline if the patient has any signs and symptoms consistent with bone metastasis or a

history of bone metastasis. Bone metastasis identified at baseline must be documented and assessed according to RECIST 1.1 at the times of the other tumour measurements indicated in the [flow chart](#). During the study bone scans should be repeated as clinically indicated in patients without bone metastasis at Baseline.

For the purposes of this study, patients should be re-evaluated for response at weeks 8, 16, 24 and every 8 weeks thereafter. In the event of a treatment delay, interruption or discontinuation of treatment, tumour assessment should continue to follow the original schedule.

Follow-up tumour assessments must utilize the same CT/MRI/photographic method and acquisition technique (including use or non-use of IV contrast) as were used for screening assessments to ensure comparability. A chest x-ray or skeletal x-ray which clearly demonstrates a new metastatic lesion may be used to document progression in lieu of CT/MRI/bone scan.

These patients will have their response classified according to the definitions stated below.

Measurability of the disease

Measurable lesions

Lesions that can be accurately measured in at least one dimension with longest diameter ≥ 10 mm (by CT scan, MRI, caliper measurement) or ≥ 20 mm (by chest X-ray). Pathological lymph nodes, defined as lymph nodes with a short axis >15 mm are also measurable.

Measurable disease

Measurable disease requires the presence of at least one measurable lesion. Measurable lesion if limited to either small (<2 cm) solitary visceral lesion or scant (<5 cm) lymph nodes only metastasis should be evaluated for additional evidence of malignant nature and discussed with BI trial clinical monitor before enrolling.

Non-measurable disease

Non-measurable lesions are all other lesions, including small lesions (longest diameter <10 mm with CT scan, MRI or caliper measurement or <20 mm with chest X-ray or pathological lymph nodes with shortest axis ≥ 10 and <15 mm) as well as truly non-measurable lesions. Lesions considered truly unmeasurable include leptomeningeal disease, ascites, pleural or pericardial effusion, inflammatory breast disease, lymphangitic involvement of skin or lung, abdominal masses/ abdominal organomegaly identified by physical exam that is not measurable by reproducible imaging techniques.

Lesions with prior local treatment

Tumour lesions situated in a previously irradiated area, or in an area subjected to other loco-regional therapy, are usually not considered measurable unless there has been demonstrated progression in the lesion

Methods of measurement

All measurements must be recorded in metric notation, using a ruler or calipers. All baseline evaluations must be performed as close as possible to the treatment start and never more than 4 weeks before the beginning of the treatment. If a lesion is considered too small to measure,

a default measurement of 5mm should be applied. If the lesion is not visible, a default measurement of 0 mm should be applied.

The same method of assessment and the same technique must be used to characterise each identified and reported lesion at baseline and during follow-up.

Clinical lesions will only be considered measurable when they are superficial (e.g., skin nodules, palpable lymph nodes). In the case of skin lesions, documentation by colour photography including a ruler to estimate the size of the lesion is obligatory.

CT and MRI are the best currently available and reproducible methods to measure target lesions selected for response assessment. Conventional CT and MRI should be performed with cuts of 5 mm or less in slice thickness contiguously. Spiral CT should be performed using a 5 mm contiguous reconstruction algorithm. This applies to the chest, abdomen and pelvis.

Ultrasound, endoscopy and laparoscopy should not be used to measure tumour lesions or evaluate tumour response. However, these techniques can be useful to supplement information from other techniques.

Cytology and histology can be used to differentiate between PR and CR in rare cases (for example, residual lesions in tumour types such as germ cell tumours where known residual benign tumours can remain).

Baseline Documentation of Target and Non-target Lesions

All measurable lesions up to a maximum of two lesions per organ and five lesions in total, representative of all involved organs should be identified as target lesions and will be recorded, measured (longest diameter = LD) and numbered at baseline. Target lesions should be selected on the basis of their size (lesions with the longest diameter) and their suitability for accurate repetitive measurements (either by imaging techniques or clinically). Lymph nodes must be ≥ 15 mm in order to be considered as target lesions.

A sum of the longest diameter (LD) for all target lesions will be calculated and reported as the baseline sum LD. The baseline sum LD will be used as reference to further characterise the objective tumour response of the measurable dimension of the disease (see table below):

Table 10.5: 1 Evaluation of target lesions

Complete Response (CR)	Disappearance of all target lesions.
Partial Response (PR)	At least a 30% decrease in the sum of LD of target lesions taking as reference the baseline sum LD.
Progression (PD)	At least a 20% increase in the sum of LD of target lesions taking as reference the smallest sum LD recorded since the treatment started, together with an absolute increase in the sum of LD of at least 5mm. OR The appearance of one or more new lesions.
Stable Disease (SD)	Neither sufficient shrinkage to qualify for PR, taking as reference the baseline SoD, nor sufficient increase to qualify for PD taking as reference the smallest SoD since the treatment started.

All other lesions (or sites of disease) should be identified as non-target lesions and should also be recorded at baseline. Measurements are not required and these lesions should be followed as “present” or “absent” (see [Table 10.5: 2](#)).

Table 10.5: 2 Evaluation of non-target lesions and new lesions

Complete Response (CR)	Disappearance of all non-target lesions and normalisation of tumour marker level. All lymph nodes must be non-pathological in size (<10 mm short axis)
Non-CR/Non-PD	Persistence of one or more non-target lesions or/and maintenance of tumour marker level above normal limits.
Progression (PD)	Appearance of one or more new lesions and/or unequivocal progression of existing non-target lesions. Although a clear progression of non-target lesions only is exceptional, in such circumstances, the opinion of the treating physician should prevail and the progression status should be confirmed later by the review panel (or study chair).

In some circumstances it may be difficult to distinguish residual disease from normal tissue. When the evaluation of complete response depends upon this determination, it is recommended that the residual lesion be investigated (fine needle aspirate/biopsy) before confirming the complete response status.

Confirmation

In case of tumour response (CR or PR), confirmation will be performed with a repeat assessment no less than 4 weeks after the RECIST criteria for response have been met. In the case of SD, measurement must have met the SD criteria at least once after study entry at an interval of not less than 6 weeks.

Evaluation of best response to study treatment

The best response to study treatment ([Table 10.5: 3](#)) is the best response recorded from the start of treatment until disease progression or start of further anti-cancer treatment (taking as reference for progressive disease the smallest measurements recorded since the treatment started). In general, the patient’s best response assignment will depend on the achievement of both measurements and confirmation criteria ([Table 10.5: 3](#)).

Patients with a global deterioration of health status requiring discontinuation of treatment without objective evidence of disease progression at that time should be reported as “symptomatic deterioration”. Every effort should be made to document the objective progression even after discontinuation of treatment.

Table 10.5: 3 Algorithm for evaluation of overall response

Target lesions	Non-target lesions	New lesions	Overall response
CR	CR	No	CR
CR	Non-CR/ Non-PD	No	PR
CR	Not evaluated	No	PR
PR	Non-PD or not evaluated	No	PR
SD	Non-PD or not evaluated	No	SD
Not evaluated	Non-PD	No	NE
PD	Any	Yes or No	PD
Any	PD	Yes or No	PD
Any	Any	Yes	PD

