## **5. ENDPOINTS**

### **5.1 PRIMARY ENDPOINT**

This is an open label, uncontrolled, exploratory phase II trial with two patient cohorts. The purpose of this trial is to assess the anti-tumour activity and safety of afatinib monotherapy in patients with urothelial tract carcinoma carrying ERBB2 or ERBB3 mutations or ERBB2 amplifications (Cohort A), and EGFR amplification positive tumours (Cohort B), progressing despite previous platinum based chemotherapy, and thereby to improve their prognosis.

Cohort A of the study follows a two stage design where an analysis for futility will be performed at the end of stage 1 to determine if the stage 2 of cohort A will be carried out. Cohort B of the study will include up to 10 patients with EGFR amplification. Analysis will be conducted in parallel to, and independent of cohort A.

The primary endpoint of this study is progression-free survival rate at six months (PFS6), as assessed at the investigative sites, in the ERBB2/ERBB3 cohort (Cohort A). Patients who are alive and progression-free at the 24-week assessment will be considered successes.

RECIST 1.1 (2) will be used to determine all response and progression endpoints.

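### Appendix 10.5 classes lymph nodes by short axis but adds their longest diameter to the target sum, so response and progression calls can shift in either direction

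*Protocol*

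**What the plan says.** Protocol Appendix 10.5 uses the short axis wherever it describes the size of a node and names an axis:

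- Measurable: "Pathological lymph nodes, defined as lymph nodes with a short axis >15 mm are also measurable".
- Non-measurable, among the listed examples: "pathological lymph nodes with shortest axis ≥ 10 and <15 mm".
- CR in the table for non-target and new lesions (Table 10.5:2): "All lymph nodes must be non-pathological in size (<10 mm short axis".

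The sentence on target nodes names no axis: "Lymph nodes must be ≥ 15 mm in order to be considered as target lesions".

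For the target lesions themselves the appendix records the longest diameter (LD) and then says: "A sum of the longest diameter (LD) for all target lesions will be calculated and reported as the baseline sum LD". In Table 10.5:1, PR is "At least a 30% decrease in the sum of LD of target lesions taking as reference the baseline sum LD". PD is a rise of at least 20% and at least 5 mm in the same sum from its smallest value. Target CR is "Disappearance of all target lesions". None of these rows treats nodes separately. The SD row refers to SoD, which the appendix does not define.

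Protocol Section 5.2 sends sites to this appendix for measurement and response rules. For tumour shrinkage, Section 5.1.2 and SAP 7.5.2 speak of target lesion diameters, whereas Section 7.3.2 speaks of longest diameters. SAP 5.1 says "RECIST 1.1 (2) will be used to determine all response and progression endpoints" and adds no nodal rule.

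**The concern.** A node is called pathological or normal on one dimension and followed on another. The two dimensions weigh the node differently against the other target lesions, so the same scans can cross the 30% or 20% threshold on one dimension and not on the other.

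The PR and PD calls feed ORR, PFS6 and PFS, and the duration of response. Tumour shrinkage is computed directly from the sum. Response is assessed by investigators at about 30 to 35 sites, and independent review is only a possibility. Different sites could reasonably resolve the conflict in different ways, and nothing in the SAP would show that they had.

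**Working it through.** **Plan's own figures.** The point disputes no stated figure. As a background check, exact binomial power at N=70 without the stage 1 adjustment is 90.9% and 94.3% for PFS6 (alpha 0.025 and 0.05), as in Table 7.7:1. For ORR it is 84.3% at both levels, against 84.2% in Table 7.7:2. These figures are unaffected.

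**Inputs.** The thresholds come from Table 10.5:1: PR is a fall of 30% or more from baseline; PD is a rise of 20% or more, and 5 mm or more, from the smallest sum. The lesion sizes are assumptions chosen for illustration, not data from the documents. Each example assumes no new lesion and no non-target progression.

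**Formula.** Let V be the sum over non-nodal targets, and let L and S be a node's longest diameter and short axis. The sum is V+L as written, or V+S with the short axis. A change d in V with the node stable gives d/(V+L) or d/(V+S). Because L is at least S, the LD sum dilutes change in the other lesions and gives the node more weight. With V=30 and a 32 x 16 mm node, the node's share of the sum is 32/62 = 51.6% by LD and 16/46 = 34.8% by short axis.

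**Mixed target disease.**

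| Case | Sum with node LD | Sum with node short axis |
|---|---|---|
| Visceral 30 to 40, node stable at 32 x 16 | 62 to 72: 10/62 = +16.1%, SD | 46 to 56: 10/46 = +21.7%, PD |
| Visceral stable at 30, node 32 x 16 to 45 x 22.5 | 62 to 75: 13/62 = +21.0%, PD | 46 to 52.5: 6.5/46 = +14.1%, SD |
| Visceral 40 to 22, node stable at 30 x 16 | 70 to 52: -18/70 = -25.7%, SD | 56 to 38: -18/56 = -32.1%, PR |

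The first two cases disagree in opposite directions. In the first, PD needs visceral growth of 0.20 x 62 = 12.4 mm by LD but 0.20 x 46 = 9.2 mm by short axis, so growth from 9.2 mm up to 12.4 mm is classed differently. In the third, PR needs shrinkage of 0.30 x 70 = 21.0 mm against 0.30 x 56 = 16.8 mm.

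**Node only.**

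- Unequal change, 28 x 18 to 21 x 9: LD -7/28 = -25.0% (SD); short axis -9/18 = -50.0% (PR), with the node now below 10 mm.
- Proportional change, 30 x 18 to 15 x 9: -50% on both axes, so no difference.

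**CR.** Visceral 25 to 0, node 28 x 16 to 16 x 8. The node is normal by the 10 mm limit but has not disappeared, so target CR fails. The LD sum goes from 53 to 16: -37/53 = -69.8%, PR. ORR counts CR and PR alike and does not change.

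**Sensitivity of the tests to one patient.** Using P(X >= s | n, p) from Sections 7.3.1 and 7.3.2 with n=70: for ORR (p=0.05), 7 responders give 0.060 and 8 give 0.023; for PFS6 (p=0.40), 35 successes give 0.057 and 36 give 0.035. At stage 1, when fewer than 12 of 25 reach PFS6, one confirmed response or two decides whether the trial stops.

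**The case against.** **RECIST 1.1 governs and the appendix is only based on it.** True, and two endpoint descriptions say diameters rather than longest diameters. But Section 5.2 sends sites to the appendix for the working rules, and naming a standard does not tell a site which of two conflicting local instructions to follow. The guideline's text is not in the documents, so this point rests on the internal conflict alone.

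**A reader might infer that nodal disease is systematically misclassified, with responses and progressions missed.** The documents do not support that. Proportional change in node-only disease gives the same percentage on either axis, and in mixed disease the error can run either way.

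**A reader might infer that the CR wording lowers ORR.** It does not; it moves patients from CR to PR. Nor is that wording a clear contradiction. Table 10.5:2 speaks of all lymph nodes, and Table 10.5:3 requires non-target CR for an overall CR, so whether the 10 mm limit covers target nodes is ambiguous.

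**A reader might infer that a node of exactly 15 mm falls into no class yet can be a target.** It does not. The non-measurable class covers all remaining lesions, and targets are drawn only from measurable ones. The >15 and >=15 mm wordings are merely untidy.

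**A reader might infer that short axes were never recorded.** The CRF is not in the documents, and images are stored, so this is unknown.

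**The one-patient p-values would apply to any reclassified patient.** This stands: they show how finely the tests are balanced, not how often nodal measurement would matter.

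**Conclusion.** The conflict is in the current text and should be corrected. Appendix 10.5 as written can change SD to PR, SD to PD or PD to SD for patients with nodal targets, and nothing in the SAP settles which dimension applies. PFS6 and ORR are exposed only through the sum-based PR and PD rules; DCR is exposed only through calls that turn on PD. No direction of bias is established.

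The size of the effect cannot be computed. It depends on the share of patients with nodal targets, the shape of the nodes and how many sums lie near a threshold, none of which the documents give. The examples show that discordance is possible at ordinary lesion sizes; they do not estimate its frequency. The trial is exploratory, which limits the consequence, but PFS6 and ORR drive both the stage 1 decision and the final tests.

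**What to change.** 1. In Appendix 10.5 and Section 7.3.2, replace the longest-diameter sum and SoD with one term: the sum of diameters, meaning longest diameter for non-nodal lesions and short axis for lymph nodes. This keeps the dimension by which the appendix already classes nodes; the sponsor should check it against the cited guideline.
2. Define target CR as disappearance of all non-nodal targets, with every target node below 10 mm short axis.
3. Use one 15 mm short-axis cut-off, with the same inequality, for measurable nodes and target nodes.
4. Instruct sites to record the short axis of nodal targets at every assessment.
5. For patients already assessed, leave the investigators' calls as made. Where short axes are recorded or can be read from stored images, report the short-axis classification of PFS6 and ORR as a sensitivity analysis.

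The cost is an edit to the appendix and Section 7.3.2, a CRF instruction, and some retrospective measurement. That measurement would be made by unblinded sites that know the outcomes, which is why it should inform a sensitivity analysis and not replace the calls. No new scans are needed.

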10.6 APPENDIX 6: NYHA CLASSIFICATION OF HEART FAILURE

Class	Patient Symptoms
Class I (Mild)	No limitation of physical activity. Ordinary physical activity does not cause undue fatigue, palpitation, or dyspnea (shortness of breath)
Class II (Mild)	Slight limitation of physical activity. Comfortable at rest, but ordinary physical activity results in fatigue, palpitation, or dyspnea.
Class III (Moderate)	Marked limitation of physical activity. Comfortable at rest, but less than ordinary activity causes fatigue, palpitation, or dyspnea.
Class IV (Severe)	Unable to carry out any physical activity without discomfort. Symptoms of cardiac insufficiency at rest. If any physical activity is undertaken, discomfort is increased.

11. DESCRIPTION OF GLOBAL AMENDMENT(S)

Number of global amendment		1
Date of CTP revision		13 MAR 2017
EudraCT number		2015-005427-10
BI Trial number		1200.261
BI Investigational Product(s)		Afatinib (Giotrif, Gilotrif)
Title of protocol		Phase II open label single arm exploratory trial of oral afatinib monotherapy following platinum failure for patients with advanced/metastatic urothelial tract carcinoma with ERBB receptor deregulation.
To be implemented only after approval of the IRB / IEC / Competent Authorities		Y
To be implemented immediately in order to eliminate hazard – IRB / IEC / Competent Authority to be notified of change with request for approval		N
Can be implemented without IRB / IEC / Competent Authority approval as changes involve logistical or administrative aspects only		N
Section to be changed		
Section to be changed		Study title
Description of change		Addition of an acronym to the trial (LUX-Bladder 1), and revision of the wording (change “deregulation” by “genetic alterations”)
Rationale for change		The addition of the name to the trial was implemented for an easier reference to this trial, while the revision of the wording was included to have amore accurate definition of the genetic characteristics.
Section to be changed		
Section to be changed		Clinical trial protocol synopsis – Methodology
Description of change		Revision of the wording referring to genetic charachteristics (change “deregulation” by “genetic alterations”)
Rationale for change		To have a more accurate definition of the ERBB alterations
Section to be changed		
Section to be changed		Clinical trial protocol synopsis – Duration of

		treatment
Description of change		Addition of the need to confirm disease progression by RECIST 1.1, and inclusion of the adverse events under a global category of “other reasons requiring treatment discontinuation”
Rationale for change		To refine the criteria about treatment discontinuation and align with project guidelines.
Section to be changed		Clinical trial protocol synopsis – Objectives and Safety criteria
Description of change		Revision of the CTCAE version used to 4.03
Rationale for change		To keep consistency throughout the protocol
Section to be changed		Clinical trial protocol synopsis – No. of patients each treatment
Description of change		Increase of the number of patients to be included in Stage 2
Rationale for change		To keep consistency with Section 7 and new statistical assumptions.
Section to be changed		Flow chart
Description of change		Addition of one visit one week after starting second course of treatment.
Rationale for change		To add a better follow up and management of potential adverse events
Section to be changed		Flow chart
Description of change		Addition of a column on description of visits after Course 3
Rationale for change		To have a better and clearer description of trial procedures
Section to be changed		Flow chart footnote #2
Description of change		Addition of the window for EoR visit
Rationale for change		To add flexibility to the conduct of this visit, and keep consistency with section 6.2.3.2
Section to be changed		Flow chart footnote #4
Description of change		Change the units of timeframe for vital status collection (from months to days)
Rationale for change		To keep consistency throughout the protocol and have all timeframes in days
Section to be changed		Flow chart footnote #5
Description of change		To clarify that after course 3 of treatment only one

		visit per cycle is required.
Rationale for change		To keep consistency throughout the protocol as a consequence of the addition of the new visit after C21V1.
Section to be changed		Flow chart footnote #7
Description of change		Addition of a comment about the need to have one more visit one week after starting course 2
Rationale for change		To add a better follow up and management of potential adverse events
Section to be changed		Flow chart footnote #15
Description of change		Clarification regarding previous image assessments obtained within 28 days of starting study treatment
Rationale for change		To add clarity on trial procedures
Section to be changed		1. Introduction
Description of change		Change ErbB1 by ERBB1, and rewording of specific parts of the text
Rationale for change		To have a more accurate definition on genetic alterations and better English wording.
Section to be changed		1.1 Medical Background
Description of change		Expansion of what TCCU stands for, better definition of genetic alterations, and updates on previous trials.
Rationale for change		To have a more accurate definition of the ERBB alterations, better English wording, and updated results on previous investigations.
Section to be changed		1.2 Drug Profile
Description of change		Update on Investigators' Brochure reference number and Giotrif approvals
Rationale for change		To update protocol on latest afatinib's documents and labelling.
Section to be changed		2.1 Rationale for performing the trial
Description of change		Update on the results of previous trials
Rationale for change		To keep protocol updated according to recent publications
Section to be changed		2.2 Trial Objectives
Description of change		Addition of a reference and rewording of parts of the section.
Rationale for change		To add clarity to this section.

Section to be changed		2.3 Benefit-risk assessment
Description of change		Revision of the AEs related to afatinib
Rationale for change		To align the protocol with latest updates on Afatinib and project requirements.
Section to be changed		3.1 Overall trial design and plan
Description of change		Revision of the wording referring to genetic characteristics and conditions for treatment discontinuation
Rationale for change		To keep consistency throughout the trial protocol
Section to be changed		3.1.1 Administrative structure of the trial
Description of change		Increase the number of participating sites
Rationale for change		This is consequence of the expansion of the trial to two additional countries in Europe
Section to be changed		3.2 Discussion of trial design, including the choice of control groups
Description of change		Revision of the text referring to the statistical analysis
Rationale for change		To keep consistency with Section 7.
Section to be changed		3.3.2 Inclusion criteria #4
Description of change		Rewording of the criteria, specifying what could be considered as one line of chemotherapy
Rationale for change		To add clarity to the criteria.
Section to be changed		3.3.2 Inclusion criteria #5
Description of change		Revision of the criteria about previous treatments
Rationale for change		To add clarity to the criteria, especially regarding the use of previous immunotherapy, which was not detailed before.
Section to be changed		3.3.3 Exclusion criteria #4
Description of change		Revision of the wording regarding previous radiotherapy
Rationale for change		To add clarity to the criteria and align to RECIST 1.1
Section to be changed		3.3.3 Exclusion criteria #8
Description of change		Addition of the incidental localized prostate cancer to previous or concomitant allowed malignancies
Rationale for change		To allow for this patients to be entered, since patients with incidental localized prostate cancer

		have good prognostic and would not need further treatment, which would interfere with treatment of urothelial cancer.
Section to be changed		3.3.3 Exclusion criteria #14 and #15
Description of change		Revision of the text referring to women of child-bearing potential
Rationale for change		To align with project standards and current international guidelines (ICH)
Section to be changed		3.3.4.1 Removal of individual patients
Description of change		Rewording of the removal criteria and addition of a text referring to potential treatment with Afatinib beyond study
Rationale for change		To add clarity to the removal criteria and align with project standards.
Section to be changed		3.3.4.2 Discontinuation of the trial by the sponsor
Description of change		Addition of one reason for trial discontinuation, and the possibility to suspend the trial after completing recruitment in stage 1.
Rationale for change		To align with project standards, and to include the possibility of suspending recruitment (after stage 1 is completed and before its analysis) when there are possibilities that the the drug is not working.
Section to be changed		4.1.4.1 Administration of Afatinib
Description of change		Revision of the duration of treatment with afatinib
Rationale for change		To keep the consistency throughout the protocol regarding the treatment duration.
Section to be changed		4.1.4.1.2:1 Dose reduction scheme for Afatinib
Description of change		Revision of the wording of the AE related to renal function to specify that only if caused by dehydration secondary to diarrhea.
Rationale for change		To update te protocol according to Afatinib safety profile and to clarify that afatinib does not cause renal failure per se (only diarrhea, that can lead to pre-renal failure). Consequently, only renal impairment related to dehydration caused by diarrhea should lead to dose reduction of Afatinib.
Section to be changed		4.2.2.3 Restrictions regarding women of child-bearing potential
Description of change		Revision of the text describing women of child-

		bearing potential and methods of birth control
Rationale for change		To align with project standards and current international guidelines (ICH)
Section to be changed		Table 4.2.3.2:1 General recommendations for prophylaxis while receiving afatinib
Description of change		Change in the table title to specify that the table refers to “dermatological AEs”
Rationale for change		In the previous version of the protocol this mention was missing.
Section to be changed		5.1.2 Secondary endpoints
Description of change		Rewording of part of the section and correction of typos.
Rationale for change		To add clarity and facilitate reading of the section.
Section to be changed		5.3 Assessment of Safety 5.3.5.1 Definitions of AEs – Intensity of AEs 5.7 Appropriateness of measurements
Description of change		
Rationale for change		
Section to be changed		5.5 Biomarker assessments
Description of change		Change of the word “biobanking” to “sample storage”
Rationale for change		Technically, BI is not intended to build a biobank because the samples will only be used for trial purposes. Therefore, wording has been adapted accordingly.
Section to be changed		5.5.1.1 Method of sample collection
Description of change		Revision of the number of required slides from tumour samples
Rationale for change		To align the protocol with the lab manual.
Section to be changed		5.5.2.1 Exploratory tumour tissue analyses
Description of change		Removal of the “mRNA expression of the ERBB receptors, their ligands and genes of relevance by technologies such as nanostring or RT PCR” and addition of the “expression of mRNAs by Next generation sequencing”
Rationale for change		To update the trial tests according to latest investigations on biomarkers in urothelial cancer.

Section to be changed		5.5.4 Biobanking
Description of change		Addition of the whole section and change of title
Rationale for change		The whole section was missing in the previous version of the protocol.
Section to be changed		6.2.1 Screening period – pre-screening visit
Description of change		Clarification regarding previous image assessments obtained within 28 days of starting study treatment
Rationale for change		To add clarity on trial procedures
Section to be changed		6.2.2 Treatment period
Description of change		Addition of a patient contact one week after starting second course of treatment
Rationale for change		To add a better follow up and management of potential adverse events
Section to be changed		6.2.3.2 End of residual effect period (EoR)
Description of change		Addition of a window for this visit
Rationale for change		To add flexibility to the conduct of this visit.
Section to be changed		6.2.3.3.1 Follow-up for progression
Description of change		Increasing of the window to perform imaging tests in this visit, from 2 days to 1 week.
Rationale for change		To add flexibility to the conduct of this visit.
Section to be changed		6.2.3.3.2 Follow-up for Overall survival
Description of change		Change the units on timeframe for vital status collection (from months to days), and rewording of the follow up visit
Rationale for change		To keep consistency throughout the protocol (to and have all timeframes in days, and to correctly name the visits according to flowchart).
Section to be changed		7 Statistical Methods and determination of the sample size
Description of change		Revision of the whole section
Rationale for change		To refine the statistical model and better describe trial hypotheses and analysis.
Section to be changed		7.3.4 Safety analysis
Description of change		Updates on the tables and listing that will be provided with these analyses
Rationale for change		To align the protocol with project standards and latest updates on Afatinib safety profile.

Section to be changed		9 References
Description of change		Addition of few publications and removal of outdated ones
Rationale for change		To update the protocol on latest published data
Section to be changed		
Description of change		10.1 Appendix 1
Description of change		Addition of the whole section and title
Rationale for change		The whole section was missing in the previous version of the protocol.
Section to be changed		
Description of change		10.2 Appendix 2: Cockcroft-Gault formula
Description of change		Remove the need to add calculation in patient's chart and rewording.
Rationale for change		All variables used for eCcr are already present in patient's chart and do not see the need to detail the calculations.
Section to be changed		
Description of change		10.4 Appendix 4: Clinical Evaluation of liver injury
Description of change		Removal of Haptoglobin from the required parameters to be obtained in case of confirmed DILI case
Rationale for change		To update the protocol according to BI standard: DILI Checklist was revised and this parameter is not longer required.
Section to be changed		
Description of change		10.5 Appendix 5: RECIST 1.1 criteria
Description of change		Revision of the text about new lesions in irradiated fields
Rationale for change		To adapt the trial protocol to the latest version of RECIST 1.1 criteria.

(Continued) Signatures (obtained electronically)

Meaning of Signature	Signed by	Date Signed
-----------------------------	------------------	--------------------
